1.3.2.2. Safety assessments

- AE(s) and SAE(s) according to the NCI-CTCAE version 4.0 scale
- Clinical laboratory tests (haematology (full blood count including red blood cells (RBC), haemoglobin, haematocrit, mean cell volume (MCV), mean cell haemoglobin (MCH), mean cell haemoglobin concentration (MCHC), white blood cells (WBC) with differential and platelet count; neutrophils, lymphocytes, monocytes, eosinophils, basophils) and biochemistry (urea, creatinine, total bilirubin, chloride, bicarbonate, sodium, potassium, calcium, inorganic phosphate, alkaline phosphatase (ALP), aspartate aminotransferase (AST), alanine aminotransferase (ALT), gamma-glutamyl transferase (GGT), albumin, total protein, total cholesterol, triglycerides, and fasting glucose)).
- Concomitant medications/therapies and non-drug therapies.
- Concomitant and surgical procedures
- Death reports

- Physical examination and vital signs (height, weight, heart rate and sitting blood pressure (systolic and diastolic).

1.3.2.3. *Other assessments*

The other assessments will be the following:

- Demography and characteristics at screening:
 - Country,
 - Race (Asian; Black/African American; Caucasian/White; Native Hawaiian/Other Pacific Islander, American Indian/Alaska Native, Multiple),
 - Date of visit,
 - Date of birth.
- Prostate Cancer History (prior to RP)
 - Date of first histological diagnosis
 - Gleason Score (Primary Pattern, Secondary Pattern, Total Score),
 - cTNM Staging (T, N, M) and method used (MRI, CT Scan, X-Ray, Transrectal Ultrasound, Clinical Judgment, Other),
 - Last available PSA level (ng/mL),
 - Last available testosterone level (ng/dL).
- Radical Prostatectomy Procedure
 - Date of surgery
 - Pelvic lymphadenectomy (Yes; No),
 - If yes, extended / not extended,
 - Gleason Score (Primary Pattern, Secondary Pattern, Total Score),
 - pTNM Staging (T, N, M).
- WHO/ECOG Performance Status Scale.
- Significant Medical or Surgical history (including ongoing medical history other than prostate cancer related).
- Prior and concomitant medications/therapies and non-drug therapies.

1.3.2.4. *Withdrawal / discontinuation from the study*

The date of early withdrawal and the primary reason for early withdrawal will be recorded (adverse event, protocol violation, consent withdrawn, lost-to follow-up, other).

1.3.2.5. *Compliance*

Compliance assessments will be the following:

- Injection triptorelin administration performed (Yes/No),

- Date of drug administration,
- Date of surgery (radical prostatectomy),
- Dose :
 - Planned volume administered (Yes/No),
 - If no, reason and volume administered (ml).

CONFIDENTIAL

RAP Final Version 3 [22-JUL-2019]

13/248

1.3.3. Schedule of assessments

Table 1. Schedule of Assessments

Visit	1	2	3	4	5	6	7	8	9	10	11	12	13	14	XX
	Screening	Baseline	3M	6M	9M	12M	15M	18M	21M	24M	27M	30M	33M	36M	Every 3M
Informed Consent	X														
Demographic Data	X														
Medical History	X														
Eligibility Criteria	X	X													
Physical Examination	X	X	X	X	X	X	X	X	X	X	X	X	X	X	X
Vital Signs		X													
ECOG/WHO Performance Status		X			X					X				X	
Randomisation		X													
Testosterone Level [a], [b]		X	X [c]	X [d]	X [d]										
Blood Chemistry and Haematology	X				X										
PSA Level [e]	X		X	X	X	X	X	X	X	X	X	X	X	X	X
Clinical Disease Progression Assessment [f]			X	X	X	X	X	X	X	X	X	X	X	X	X

CCI

CONFIDENTIAL

RAP Final Version 3 [22-JUL-2019]

14/248

Visit	1	2	3	4	5	6	7	8	9	10	11	12	13	14	XX
FACT-P Questionnaire		X			X					X				X	
SF-36 Health Survey		X			X					X				X	
Triptorelin Injection [a]		X	X	X											
Prior and Concomitant Medication/Therapy	X	X	X	X	X	X	X	X	X	X	X	X	X	X	X
Prior and Concomitant Non-Drug Therapy	X	X	X	X	X	X	X	X	X	X	X	X	X	X	X
AEs [1]	X	X	X	X	X	X [1]									
Visit Status	X	X	X	X	X	X	X	X	X	X	X	X	X	X	X

AE, adverse event; CCI, prostate specific antigen; ECOG, Eastern Cooperative Oncology Group; FACT P, functional assessment of cancer therapy prostate; M, month; PSA,

CC1

- a Only for the triptorelin adjuvant treatment group (± 7 days)
- b Always prior to each triptorelin injection (Baseline, 3 months, and 6 months)
- c Evidence of lack of castration at 3 months/Visit 3 will be documented by serum testosterone ≥50 ng/dL (≥0.50 ng/mL) confirmed by a second elevated serum testosterone level at least two weeks later. For the other testosterone assessment time points (Baseline, and 6 and 9 months), no confirmation test is required.
- d If evidence of lack of castration at 3 months/Visit 3, therefore testosterone sampling is not required anymore at Visit 4/Month 6 and Visit 5/Month 9.
- e Starting from Visit 3, any elevated PSA concentration >0.2 ng/mL should be confirmed by a second measurement performed 4 to 6 weeks later. No confirmation test is required after evidence of disease progression (biochemical relapse (BR) and/or clinical disease progression).
- f Clinical disease progression assessments (such as ultrasound [US] guided-biopsy, X-ray, computed tomography [CT] scan, magnetic resonance imaging [MRI]) can be performed at any time during the study at the Investigator's discretion and as per local standard care.

CC1

CONFIDENTIAL

RAP Final Version 3 [22-JUL-2019]

15/248

CCI

1 Adverse events (AEs) will only be collected until Visit 5/Month 9; this corresponds to three months after the last triptorelin injection for those patients in the triptorelin group. After this visit, only AEs and SAEs related to triptorelin according to Investigator's judgement should be reported (with the exception of AEs resulting in death that should be reported until the end of the study).

Patients will not be withdrawn from the study if study medication is discontinued. Follow-up will continue for all patients every 3 months and for at least 36 months.

1.3.4. *Planned sample size*

It is planned to recruit 226 patients in approximately 10 centres in two countries (China and Russia) according to the Sample Size Determination.

The sample size estimation was based on the primary efficacy endpoint of BRFS. Assuming that with RP alone, the probability of biochemical (PSA) relapse as defined in Section 4.2.1 of the study protocol at 36 months after RP is 40% in high-risk patients (Section 2.1 of the study protocol, Table 1), and anticipating that immediate adjuvant hormonal therapy added to RP will reduce this probability to 20% (percentage considered to be clinically relevant), 113 patients per treatment group (226 in total) are required in order to detect such a difference using a two-sided log-rank test at a significance level of 5% and a power of 90%, assuming a common 1% exponential dropout rate (corresponding to an approximate 5% dropout rate per year).

These 226 patients are required to observe 61 BR in order to achieve 90% power. For patients with no sign of disease progression at 36 months post-randomisation, monitoring will continue until the 61 BR events are observed at the study global level. If the 61 events are observed before all patients complete the 36 months post-randomisation monitoring period, the study will be continued until those patients reach their 36 month visit (Visit 14).

2. PATIENT POPULATIONS (ANALYSIS SETS)

2.1. Screened population

The screened population is defined as all patients with Visit 1 (Screening, Day - 14) performed and who have given informed consent.

2.2. Enrolled population

The enrolled population is defined as all patients from the screened population with visit 2 (Baseline, Day 1) performed.

2.3. Randomised population

The randomised population is defined as all patients from enrolled population who were randomised (i.e. with a randomisation number).

2.4. Safety population

The safety population (SS) is defined as all randomised patients that have received at least one injection for patients from the triptorelin arm or that have undergone at least one day of active surveillance for patients from the active surveillance arm (patient that attended at least one visit after Visit 2 (Baseline, Day 1) or with at least one collected safety data). The patients will be analysed according to the treatment received.

2.5. Intention-to-treat population

The Intention-to-treat population (ITT) is defined as all randomised patients analysed according to the group to which they were randomised (i.e. regardless of treatment approach followed).

2.6. Modified ITT population

The Modified ITT (mITT) is defined as all patients in the ITT population excluding those not treated or without any visit after Visit 2 (Baseline, Day 1). The patients will be analysed according to the group to which they were randomised (i.e. regardless of treatment approach followed).

2.7. Per Protocol population

The Per Protocol (PP) population is defined as all patients in the mITT population for whom no major protocol violations/deviations occurred.

Definition of protocol deviations will be managed in a separate document.

The final status of deviations (minor/major) will be finalized during a blind data review meeting.

Listings of patients regarding inclusion in each population (i.e. satisfying the population definition) and associated data will be reviewed by the study team. Data will be excluded from the PP population on a patient basis and not on a visit basis. Reasons for exclusion from PP population will be presented in a summary table.

2.8. Primary populations

Baseline data (medical history, concomitant disease (pre-treatment AEs and ongoing medical history, prior medications and therapies, baseline symptoms etc.)) will be presented by treatment group and overall for the ITT population. Baseline and demographics characteristics will be repeated on the safety population if there is at least 10 % difference between the safety and the ITT population

The analysis based on the primary efficacy endpoints will be performed on ITT, mITT and PP populations. mITT and PP analyses will only be considered as exploratory.

The secondary efficacy endpoints will be analysed on the ITT population.

The analyses of safety data will be performed on the safety population.

3. STATISTICAL METHODS

3.1. Statistical analysis strategy

All statistical analyses will be performed by the biostatistics unit of AIXIAL using the Statistical Analysis System® (SAS®) software version 9.4 (SAS Institute Inc., Cary, North Carolina, USA).

The statistical analyses will be performed in accordance with International Conference on Harmonisation (ICH) E9 guideline.

3.1.1. Primary efficacy endpoint

BRFS is defined for each patient by the period in months of time from randomisation to time of Biochemical Relapse.

3.1.2. Secondary efficacy endpoint(s)

The secondary efficacy endpoints are:

- EFS (defined for each patient as the period of time (in months) from randomisation to time of first clinical disease progression or death from any cause).
- OS (defined for each patient as the period of time (in months) between randomisation and death from any cause).

- Disease-specific mortality (measured as the time (in months) between randomisation and death related to prostate cancer).
- PSADT (defined as the time (in months) from the first documented PSA increase >0.2 ng/mL to the time of the first value more than twice that of the first increased value).
- PSA level at each visit.
- Serum testosterone in the triptorelin treatment group at baseline, 3, 6 and 9 months.
- HRQoL (assessed using the Assessment of Cancer Therapy – Prostate (FACT-P) questionnaire, version 4, and the 36-item short form (SF-36) health survey, version 2) in both treatment arms at baseline, 9, 24 and 36 months.

3.1.3. *Safety endpoint(s)*

The safety endpoints are:

- Signs and symptoms, incidence and severity of all AE(s) regardless of relationship to the study drug graded according to the NCI-CTCAE version 4.0 scale including SAEs and treatment discontinuations due to toxicity.
- Clinical laboratory tests
- Concomitant medications and non-drug therapies
- Concomitant and surgical procedures

3.1.4. *Multiplicity*

No adjustment for multiplicity will be performed.

3.1.5. *Significance testing and estimation*

All statistical tests will be performed two-sided with a type I error rate set at 5%.

Quantitative variables will be summarised in statistical tables indicating the number of non missing observations (n), the mean and standard deviation (SD), the two-sided 95% confidence interval (CI) of the mean, the median, the quartiles (Q1 and Q3), the minimum and maximum.

Qualitative variables will be summarised in statistical tables indicating the number of non missing observations (n), frequency, percentage of each modality and the two-sided 95% CI associated.

For all parameters, the number of missing values will also be reported in the tables, but they will not be counted for the percentage calculation (qualitative data).

Time to event data will be analysed using Kaplan-Meier method to obtain the estimates of survival median, their associated 95% CI, survival curves for each treatment group and log-rank test p-value will be provided for treatment comparison. The Cox Proportional hazard model will be fitted to compute hazard ratios and the corresponding 95% CI.

All quantitative variables will be analysed with either analysis of variance (ANOVA) or analysis of covariance (ANCOVA) adjusting for baseline when measured. Treatment effect estimates (differences between treatment groups) will be provided with their associated 95% CI.

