1.3.2.1. Efficacy assessments

PSA

Blood samples for PSA testing will be taken every 3 months (except at Visit 2 (Baseline, Day 1 Month 0) where PSA level is not required).

Biochemical Relapse

Biochemical Relapse definition: increased PSA >0.2 ng/mL confirmed by a second measurement performed 4 to 6 weeks later. The time-point at which the first elevated PSA measurement is >0.2 ng/mL is recorded will be deemed to be the time of BR.

To note, for the identification of BR; all PSA samples will be taken into account, even if several samples are within the same time windows.

Clinical disease progression

Clinical disease progression is defined as evidence of local/locoregional recurrence and/or lymph node involvement and/or distant metastases documented by relevant standard investigations (such as ultrasound (US) guided biopsy, X-ray, computed tomography (CT) scan, or magnetic resonance imaging (MRI) guided biopsy).

Survival status

Survival status will be recorded at each visit.

Serum Testosterone

Serum testosterone in the triptorelin treatment group will be recorded at baseline, 3, 6 and 9 months. It will be assessed both as a continuous and as a qualitative variable (< 50 ng/dL / ≥ 50 ng/dL).

Health-Related Quality of Life

Health-Related Quality of Life (HRQoL) will be assessed using the FACT-P questionnaire, version 4, and the 36-item short form (SF-36) health survey, version 2 in both treatment arms at Baseline, 9, 24, and 36 months..

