3.2.1.2. Secondary efficacy analysis

The secondary efficacy analyses will be performed on the ITT population. In these analyses, no interaction will be tested for EFS, OS, disease-specific mortality and PSA doubling time. For serum testosterone, only patients in the triptorelin-treated group will be included in the analysis

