3.2.1.2.4. PSA Doubling Time

PSADT will be provided by treatment group (cf. Section 3.2.10 for derived PSADT).
PSADT will be compared between groups using the same analysis and strategy used for BRFS.

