Compliance

Time between first drug administration and RP (weeks) will be derived as $(\text{Date of first drug administration} - \text{Date of radical prostatectomy} + 1) / 7$.

Time between each drug intake (weeks) will be derived as $(\text{Date of drug intake at Visit } t - \text{Date of drug intake at visit } t-1 + 1) / 7$.

Partial dates of treatment will be imputed to calculate times:

- If the day is missing and month is present the 15 of the month will be used.
- If year is present and day and month are missing then the difference between years will be used.

Changes from baseline

Changes from baseline will be calculated as a difference from baseline (e.g. assessment at the visit – assessment at baseline).

Length of patient exposure in the study

Length of patient exposure in the study (months) will be calculated as [(Date of last visit attended – informed consent date) + 1] / 30.4375.

Duration of study drug exposure

Duration of study drug exposure (months) will be calculated as [(Date of last drug administration – Date of first drug administration) / 30.4375] + 3.

Adverse event

Time to onset of AE (days) = AE start date – date of randomisation.

Duration of AE (days) = (AE resolution date – AE start date) + 1.

Time-to-event criteria

BRFS (months) will be derived as (Date of first BR – date of randomisation + 1) / 30.4375.

EFS (months) will be derived as (Date of clinical disease progression or death from any cause – date of randomisation + 1) / 30.4375.

OS (months) will be derived as (Date of death from any cause – date of randomisation + 1) / 30.4375.

Disease specific mortality will be derived as (Date of death related to prostate cancer – date of randomisation + 1) / 30.4375.

PSADT (months) will be derived as (Date of sample when the first PSA value > than twice that of the first increased value – Date of sample of the first PSA value increased value (i.e. > 0.2 ng/mL) + 1) / 30.4375.

All of these time-to-event variables will be rounded to 1 decimal.

For BRFS, EFS, OS and Disease specific mortality, if the date of event or censor is prior to the date of randomisation, the data of event or censor taken into account will be the date of randomisation.

Rules for time-to-event data

The following table defines the rules for censoring data (for Kaplan-Meier analysis)

- BRFS

Event	Decision	Date of event or censor to consider for analysis
BR	Not censored	Date of BR (i.e. date of the first elevated PSA measurement is >0.2 ng/mL*)

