Event	Decision	Date of event or censor to consider for analysis
Clinical disease progression or death from any cause	Not censored	Date of clinical disease progression or death
No clinical disease progression and no death and no premature withdrawal from the study	Censored	Date of last visit
No clinical disease progression no death and patient premature withdrawal from the study or lost to follow-up	Censored	Date of withdrawal from the study or last contact

- OS

Event	Decision	Date of event or censor to consider for analysis
Death from any cause	Not censored	Date of death
Patient alive and no premature withdrawal from the study	Censored	Date of last visit
Patient premature withdrawal from the study or lost to follow-up	Censored	Date of withdrawal from the study or last contact

- Disease-specific mortality

Event	Decision	Date of event or censor to consider for analysis
Death related to prostate cancer	Not censored	Date of death
Death not related to prostate cancer	Censored	Date of death
Patient alive and no premature withdrawal from the study	Censored	Date of last visit
Patient premature withdrawal from the study or lost to follow-up	Censored	Date of withdrawal from the study or last contact

- PSADT

Event	Decision	Date of event or censor to consider for analysis
First PSA value > than twice that of the first increased value (> 0.2 ng/mL)	Not censored	Date of sample when the first PSA value > than twice that of the first increased value
No PSA value 2 times higher than the first increased value or no increased value and no premature withdrawal from the study	Censored	Date of last evaluable sample
Patient premature withdrawal from the study or lost to follow-up	Censored	Date of last evaluable sample before withdrawal from the study or last contact

Incomplete dates for time-to-event analyses will be handled as follows:

- If the day of the randomisation is missing and month is present, the 15 of the month will be used.
- If the day of the BR, clinical progression or death is missing and month is present, the 01 of the month will be used.
- If the month (or the date) of the death is missing, the date of the last contact will be used.
- The other dates with missing month will be studied case by case.

Castrated patients

A patient will be considered as:

- Castrated if the testosterone level is inferior to 50 ng/dL for the test or confirmation test.

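### PSA doubling time starts at the first PSA >0.2 ng/mL even if the retest refutes it, and men who never rise are censored without a time origin

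*SAP*

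**What the plan says.** SAP Section 3.1.2 lists PSADT as a secondary endpoint, measured "from the first documented PSA increase >0.2 ng/mL to the time of the first value more than twice that of the first increased value". Section 3.2.10 repeats this start in the formula, "Date of sample of the first PSA value increased value (i.e. > 0.2 ng/mL", and in the event row of the PSADT censoring table, "First PSA value > than twice that of the first increased value (> 0.2 ng/mL". None of the three asks for confirmation.

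BR is different. Section 1.3.2.1 defines it as "increased PSA >0.2 ng/mL confirmed by a second measurement performed 4 to 6 weeks later". Note e to Table 1 (Section 1.3.3) and Section 3.2.12 call for a retest of elevated values, so the confirming or refuting result is already collected.

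The PSADT censoring row in Section 3.2.10 covers "No PSA value 2 times higher than the first increased value or no increased value and no premature withdrawal from the study" and censors at the last evaluable sample. On method, Section 3.2.1.2.4 states that "PSADT will be compared between groups using the same analysis and strategy used for BRFS", i.e. Kaplan-Meier, log-rank and Cox. On population, Section 3.2.1.2 states that "The secondary efficacy analyses will be performed on the ITT population".

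**The concern.** The retest exists because a single PSA just above 0.2 ng/mL may not last. BR uses it and PSADT ignores it. A programmer following Section 3.2.10 starts the doubling clock on a rise that the trial's own retest has refuted, with two consequences:

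- If no doubling follows, the man contributes censored follow-up that is not doubling time.
- If he truly relapses later, the relapse-free interval is counted as doubling time.

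Men who stay relapse-free have more PSA tests at which a transient rise can occur. The share of false clock starts can therefore differ between arms even when relapsed men in both arms double at the same speed. The log-rank and Cox comparison could then show a PSADT difference that reflects relapse rates and assay noise.

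The censoring row adds a second problem. A man with no increased value has no start date under the formula, yet the row gives him a censoring date.

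**Working it through.** **Inputs from the SAP.** 113 patients per arm; BR at 36 months 40% versus 20%; two-sided 5%, 90% power; about 5% dropout per year (all Section 1.3.4). PSA schedule: "Blood samples for PSA testing will be taken every 3 months". Participation of at least 36 months (Section 1.2.2).

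**Assumptions not in the SAP.** The same doubling-time distribution in both arms, and a transient-rise probability per test, which is varied because the SAP gives none.

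**1. The plan's own figure.** HR = ln(0.80)/ln(0.60) = 0.437. Schoenfeld events = 4 × (1.960 + 1.282)² / (ln 0.437)² = 61.3, against the stated 61; power at 61 events is 89.9%. The design inputs are thus read correctly. With exponential relapse rate λ and dropout rate δ, the expected BR proportion by 36 months is λ/(λ+δ) × [1 − exp(−36(λ+δ))]. Here δ = −ln(0.95)/12 = 0.00427 per month, and λ = 0.01419 (control) or 0.00620 (triptorelin). This gives about 42.2 + 21.0 = 63.2 relapsed men, the number who would start a confirmed clock.

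**2. Two cases under the rule as written.**
- Refuted rise at Month 6, no relapse, last sample at Month 36: censored at 36 − 6 = 30 months.
- Refuted rise at Month 6, true relapse at Month 30: at least 30 − 6 = 24 months counted before any doubling can be observed.

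**3. Simulation among men with a rise, true doubling times equal.** Set A: follow-up to Month 36, median doubling time 8 months, log-SD 0.7, three runs of 700, 1,000 and 1,500 trials. Set B: follow-up 36 to 60 months, median 9 months, log-SD 0.6, 200 trials per setting. HR is for doubling, triptorelin over control. A dash means not run.

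| Transient rises per test, control / triptorelin | Set A, false rejection | Set B, HR and false rejection |
|---|---|---|
| 0.2% / 0.2% | – | 0.84; 10% |
| 0.5% / 0.5% | 9%, 10.6%, 11% | 0.78; 15% |
| 1% / 1% | 17.9%, 19.5%, about 20% | 0.66; 30% |
| 2% / 2% | – | 0.59; 46% |
| 0.5% / half of control | 5.3% | – |
| 1% / half of control | 6.4% | 0.94; 6.5% |
| 0.5% / 0.5%, none on triptorelin to Month 9 | 6.6% | – |
| 1% / 1%, none on triptorelin to Month 9 | 6.3%, 7.6% | – |
| 0.5% / 0.5%, none on triptorelin to Month 12 | 4.9% | – |
| 1% / 1%, none on triptorelin to Month 12 | 5.4%, 6.0% | – |
| 1% / 0.25% | – | 1.15; 7% |
| 2% / 0.5% | – | 1.18; 8.5% |
| Confirmed start | about 4–6% | 0.97–1.06; 3.5–8% |

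Monte Carlo error (95%) is about ±2 points for the 700-trial run and ±3 to 7 points for Set B.

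In Set A the number of clock starts rises from 63 to 71–72 at 0.5% per test and to 79 at 1%. At 1% in both arms, 19% of control starts and 35% of triptorelin starts are transient. With none on triptorelin to Month 12, the shares are still 19% and 25%.

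**4. Men with no rise kept as censored.** The SAP gives no origin for them, so randomisation is assumed. With no transient rises at all, rejection is 80% (Set A) and 86.5% (Set B). Adding transient rises hardly changes this: 78–79% in Set A and about 83–90% in Set B, with HR about 0.41–0.44. That is close to the design HR for relapse, 0.437.

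**The case against.** **A transient rise is not entered as a long doubling time.** Correct for a man who never doubles: Section 3.2.10 censors him. Only a refuted rise followed by true relapse gives a long observed time. The censored times still stretch the Kaplan-Meier curve.

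**A reader might infer that the rule manufactures a PSADT benefit for triptorelin.** The SAP does not support that as a general statement. It needs similar transient-rise rates per test in both arms. One arm is under castrating treatment for the first 9 months, so equal rates cannot be assumed. With lower rates there the inflation nearly disappears, and with much lower rates the direction turns against triptorelin.

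**The figures for men with a rise are not the plan's ITT analysis.** This also stands. Section 3.2.1.2 specifies ITT, and the censoring row keeps men who never rose. Under that reading transient rises matter little, because the missing time origin dominates.

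**Section 3.2.3.3 plans a PSA outlier search before database lock.** This does not cure the problem. A refuted value slightly above 0.2 ng/mL need not be an outlier, and no rule there says that it does not start the PSADT clock.

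**A reader might also want the BR date reworded.** That is not needed. Section 1.3.2.1 already ties BR to confirmation.

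**The consequence is limited.** PSADT is one of several secondary endpoints, tested without multiplicity adjustment (Section 3.1.4). The primary BRFS analysis is unaffected.

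**Conclusion.** The point holds as a definition defect with conditional impact. All three places that define PSADT start the clock without confirmation, so a refuted rise adds time that is not doubling time, whatever its frequency.

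Size and direction depend on a transient-rise rate that the SAP does not give. Among men with a rise and with equal true doubling times:

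- Equal rates in both arms: false rejection of about 9–15% at 0.5% per test and 18–30% at 1%, favouring the arm with fewer relapses.
- Rises halved under triptorelin, or absent there to Month 9 or 12: about 5–8%.
- Rises much rarer under triptorelin: the direction reverses.

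If men with no rise are kept, with an origin at randomisation (an assumption), the test largely compares relapse rates and rejects in about 80–90% of trials even without transient rises. As written, a significant PSADT result in either direction could not be read as a difference in doubling time. This should be corrected before the analysis.

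**What to change.** In Section 3.1.2 and in the PSADT formula and censoring table of Section 3.2.10:

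1. Define PSADT only for patients with confirmed BR, starting at the first PSA of the confirmed pair.
2. State that a rise not confirmed on retest does not start the clock.
3. Delete the alternative in the PSADT censoring row that covers patients with no increased value.

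The cost is SAP wording and one derivation. The retest results are already collected, so no new data are needed. The downside is that fewer patients contribute: about 63 by Month 36 under the plan's own assumptions, against 71–79 clock starts with transient rises at 0.5–1% per test. The comparison is then among relapsed patients only, a group defined after randomisation, and Section 3.2.1.2.4 should describe it as such instead of presenting it as an ITT comparison.
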